#### *Variables for consideration:*

- Number of patients
- Pre- and post-bronchodilator spirometry measurements

### 2. Assess longitudinal variation in plasma fibrinogen between individuals and within individuals over 3 years.

#### *Analyses:*

The purpose in assessing the longitudinal variation in plasma fibrinogen is to determine if patients can be meaningfully categorized into groups of those with 'high' and normal levels of fibrinogen for a duration corresponding to the likely maximum duration of most Phase 2 or Phase 3 COPD trials. A single fibrinogen measurement may be a suitable indicator of fibrinogen levels over a time period relevant to a clinical trial if it can be determined that the variability among fibrinogen measurements is not clinically important over time. Longitudinal data are required to assess intra-patient variability in fibrinogen levels over time and to help determine the stability of plasma fibrinogen concentration. Analyses assessing the stability of fibrinogen over time will be performed in ECLIPSE, the only study with longitudinal fibrinogen measurements.

Histograms will be used to present the initial fibrinogen levels of patients in the integrated database and individual studies. Additional histograms will also be presented in these samples, and fibrinogen distributions will be presented for patients with and without the presence of an outcome during follow-up (i.e., a hospitalized COPD exacerbation within 12 months, or mortality within 36 months). For histograms stratified by the presence of an outcome of interest during follow-up, the non-parametric Kolmogorov-Smirnov (KS) two-sample test statistic and corresponding p-value is also presented. This test compares the location and shape of the distribution of fibrinogen at baseline between subjects with and without outcomes. A statistically significant p-value ( $<0.05$ ) indicates the two samples are derived from populations with a different distribution.

These histograms will help to inform the choice of threshold by identifying the distribution of fibrinogen measurements; the mean, geometric mean, median, and interquartile range of fibrinogen measurements in this cohort of patients will also be calculated. A logistic regression model using any exacerbation as an outcome and baseline fibrinogen levels as the independent variable will be used to determine if the fibrinogen threshold is associated with future COPD exacerbations. The purpose of these analyses is to assess the intra-patient variability of longitudinal fibrinogen measurements and not to identify the final fibrinogen threshold. For the purposes of this analysis, fibrinogen will be considered to be a stable biomarker if there is not an appreciable difference in the number of patients who are categorized as having high fibrinogen at the initial fibrinogen measurement when compared to subsequent measurements within 3 years.

We will compare the n and % of patients classified as having high fibrinogen at baseline with those classified as high fibrinogen at subsequent visits within 3 years. If fibrinogen is a stable biomarker, a similar n and % of patients will be categorized as having high fibrinogen at subsequent visits when compared to the initial measurement. Misclassification (error) rates, sensitivity, and specificity at each threshold of fibrinogen will also be calculated for this analysis.

The frequency of patients categorized as having high or low fibrinogen at each time point during the ECLIPSE study will also be tabulated. This analysis requires the exclusion of patients who are missing fibrinogen measurements at any time point for reasons which include death or other loss-to-follow-up. As such, patients with missing fibrinogen measurements are not randomly missing. The summary of loss to follow up due to mortality or other causes will also be summarized with these analyses for reference. This analysis will be repeated for each fibrinogen threshold assessed.

Scatter plots will also be generated using data from ECLIPSE to graphically present the level of fibrinogen at baseline and subsequent time points (6 months, 1 year, 2 years, and 3 years). Pearson correlation coefficients will be calculated to assess the correlation between baseline and subsequent fibrinogen levels at each time point.

A categorical analysis of variance (ANOVA) will be used to assess the variability of fibrinogen over time. Analyses will be performed using ECLIPSE data, using the temporary threshold as defined previously, within time periods of 3 years. PROC CATMOD will be used for the categorical analysis at multiple visit lengths. To perform an analysis of variance, only subjects with continuous visits are kept.

*Variables for consideration:*

- Gender
- Fibrinogen values

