## General Statistical Considerations

This is a retrospective database analysis of previously collected data from prospective clinical trials and observational studies. These data offer an opportunity to evaluate the relationship between plasma fibrinogen and adverse COPD outcomes by pooling data from multiple sources. Analyses will be conducted separately for individual studies and integrated as indicated. Data will be pooled across the

data sources as deemed appropriate for the analysis being conducted to uphold model assumptions and per variables available within each study.

Adverse COPD outcomes that will be assessed in these analyses include COPD exacerbations and all-cause mortality. The primary endpoint of clinical trials for COPD medications is a hospitalized COPD exacerbation; however, all-cause mortality does hold clinical importance in both the conduct of clinical trials and the overall management of any chronic disease.

As the data are analyzed, some deviation from the analyses outlined is anticipated (e.g., due to missing data; small sample sizes). In instances where these deviations would make the proposed analyses inappropriate, modifications to the analysis plan will be made in consultation with the CBQC and noted in the final report.

SAS statistical software version 9.2 (SAS Institute Inc., Cary, NC) will be used to conduct the analyses. All statistical tests will be two-sided and use a significance level of 0.05 unless otherwise noted. No adjustments for multiple comparisons will be performed unless otherwise noted. For all analyses, missing data will be considered randomly missing, and no data imputations or other algorithms for missing responses will be performed unless otherwise indicated. For certain procedures (such as analysis of variance) subjects with missing data will be excluded from the analysis.

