### Currently Available Data

The currently available data includes the following studies:

1. Atherosclerosis Risk in Communities (ARIC) study: A US general population-based study begun in 1987 (The ARIC Investigators, 1989). The study recruited 15,792 participants in four communities: Forsyth County, NC; Minneapolis, MN; [name]; and Jackson, MS. Plasma fibrinogen and spirometry (non-bronchodilator) were collected at baseline.
2. Cardiovascular Health Study (CHS): A general population-based study of US participants aged 65 years and older (Fried et al., 1991). The study was initiated in 1988. The original CHS cohort comprised 5201 subjects recruited from four communities: Forsyth County, NC; Pittsburgh, PA; Sacramento County, CA; and [name]. Plasma fibrinogen and spirometry (non-bronchodilator) were assessed at the baseline visit.
3. Evaluation of COPD Longitudinally to Identify Predictive Surrogate End-points (ECLIPSE): A 3-year prospective, observational study conducted in 46 sites in 12 countries (Vestbo et al., ERJ). The ECLIPSE cohort included 2164 COPD subjects with moderate to very severe COPD (GOLD stages II, III, and IV) along with smoking and non-smoking control groups (Agusti et al., 2010). Only the COPD subjects will be included in the proposed analysis. Plasma fibrinogen was measured at baseline and longitudinally during the 3 years of ECLIPSE.
4. Framingham Heart Study (FHS) Offspring Cohort: A non-randomized cohort study initiated in 1971 (Kannel et al., 1979). Over the ensuing decades, several follow-up examinations were conducted. The cohort initially consisted of 5124 subjects (all subjects were offspring or spouses of offspring of participants in the original Framingham Heart Study). Plasma fibrinogen and

pre-bronchodilator spirometry were collected beginning with exam visit 5 of the offspring cohort study with follow-up hospitalization and vital status information available for a 25-year period. In contrast to several of the other studies proposed for inclusion, longitudinal measurements of plasma fibrinogen and lung function are available from two subsequent exam visits.

5. National Health and Nutrition Examination Survey (NHANES) III: A general population-based cross-sectional study of a representative sample of the US population. Plasma fibrinogen concentration and spirometry (pre-bronchodilator) are available from 8342 adults aged 40 years and above.

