## ASSESSMENT OF KEY ASSUMPTIONS

The use of this integrated dataset to accomplish the study objectives is predicated upon at least 2 assumptions:

1. Pre- and post-bronchodilator spirometric measurements each can be used to identify patients with COPD. Both measures are available only in the ECLIPSE and COPDGene studies. Utility of other studies requires the assumption that differences between pre- and post-bronchodilator measurements are not clinically important and that similar results are obtained using either method of defining COPD.
2. Most patients categorized at baseline as having 'high fibrinogen' maintain this classification during a period relevant to the conduct of a clinical trial.

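### The stability criterion compares how many patients are 'high' at each visit, so it does not test whether the same patients stay high

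*SAP*

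**What the plan says.** The second key assumption in the SAP's Assessment of Key Assumptions is that most patients classed as high at baseline "maintain this classification during a period relevant to the conduct of a clinical trial". Analysis 2 of that section, on longitudinal variation, gives its purpose as assessing variability within patients.

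The verdict is then defined as follows: "fibrinogen will be considered to be a stable biomarker if there is not an appreciable difference in the number of patients" classed as high at the first measurement compared with later ones within 3 years. The next paragraph says how this is applied: if fibrinogen is stable, "a similar n and % of patients will be categorized as having high fibrinogen at subsequent visits when compared to the initial measurement". No limit is set for an appreciable difference.

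The same analysis also plans error rates, sensitivity and specificity at each threshold, a tabulation of high/low status at each time point, scatter plots, Pearson correlations at 6 months and 1, 2 and 3 years, and a PROC CATMOD analysis. No criterion is attached to any of these.

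On missing data, the SAP says of the time-point tabulation: "This analysis requires the exclusion of patients who are missing fibrinogen measurements at any time point". For the CATMOD analysis it says: "To perform an analysis of variance, only subjects with continuous visits are kept". It acknowledges that the patients lost are not missing at random. General Statistical Considerations states: "For all analyses, missing data will be considered randomly missing".

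On data sources, Analysis 2 calls "ECLIPSE, the only study with longitudinal fibrinogen measurements", and Table 1 enters No for Framingham. Currently Available Data says that in Framingham "longitudinal measurements of plasma fibrinogen and lung function are available from two subsequent exam visits".

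**The concern.** The assumption is about individuals: does a patient who is high today remain high? The criterion is about totals: are about as many patients high later as at the start? Two visits can have identical totals while a large share of patients leave the high group and an equal number replace them. The stated rule cannot tell that situation from one in which nobody moves.

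This matters because the database is being analysed to support fibrinogen as a marker for selecting trial patients, and the SAP names persistence of the high class as one of two assumptions on which use of the data depends. A verdict of 'stable' reached by the stated rule would not be evidence for that assumption. A verdict of 'not stable' could also be wrong, if the whole distribution moved and patients kept their order.

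**Working it through.** The SAP states no figure for this rule, so there is none to reproduce.

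**Inputs.** From the SAP: the rule itself, and 2,118 ECLIPSE COPD subjects (Table 1), used only to scale the illustration and taken as if all were measured at both visits. Assumed, because the SAP gives neither: the share high, *p* (20%, 50%, 80%), and the correlation between baseline and follow-up, *r* (0 to 0.9). The model is bivariate normal with the same distribution at both visits.

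**Formulas.** Let P11 be the probability of being high at both visits.
- Expected number high: n × p at each visit. This does not contain *r*, so the expected difference in counts is zero for every *r*.
- Retention (share of baseline-high still high) = P11 / p. At p = 0.5 this is 1/2 + arcsin(r)/π. For example, r = 0.5 gives 1/2 + (π/6)/π = 0.667.
- Specificity (share of baseline-low still low) = (1 − 2p + P11) / (1 − p).
- Kappa with equal margins = (retention − p) / (1 − p).

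**Results.**

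| Share high | r | Expected high, each visit | Retention | Specificity | Kappa |
|---|---|---|---|---|---|
| 50% | 0 | 1,059 | 0.500 | 0.500 | 0 |
| 50% | 0.5 | 1,059 | 0.667 | 0.667 | 0.333 |
| 50% | 0.7 | 1,059 | 0.747 | 0.747 | 0.494 |
| 50% | 0.9 | 1,059 | 0.856 | 0.856 | 0.713 |
| 20% | 0 | 424 | 0.200 | 0.800 | 0 |
| 20% | 0.5 | 424 | 0.436 | 0.859 | 0.295 |
| 20% | 0.9 | 424 | 0.750 | 0.937 | 0.687 |
| 80% | 0 | 1,694 | 0.800 | 0.200 | 0 |
| 80% | 0.5 | 1,694 | 0.859 | 0.436 | 0.295 |
| 80% | 0.9 | 1,694 | 0.937 | 0.750 | 0.687 |

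At 50% high and r = 0, about 530 of the 1,059 baseline-high patients leave the group and about 530 others enter it. At r = 0.5 it is 353 each way, and at r = 0.9 it is 152.

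**Chance variation.** With fully independent visits, n = 2,118 and 50% high, the standard error of the difference in share high is √(2 × 0.25 / 2,118) = 1.54 points. The mean absolute difference is 1.54 × √(2/π) = 1.2 points and the 95th percentile is 1.96 × 1.54 = 3.0 points. A marker with no persistence at all would normally show only a small difference in totals.

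**The opposite error.** If every patient's value rises by 0.25 SD, a share of 50% becomes Φ(0.25) = 60%. The totals differ by 10 points although no patient has changed rank.

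**Why retention alone is not enough.** Under independence, retention equals *p*. At 80% high it is 80% by chance alone, with kappa 0 and specificity 20%. It must be read with one of those.

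**The case against.** The strongest reply is that the analysis as a whole would not hide instability. Sensitivity, specificity and error rates are planned in the same paragraph that applies the count rule, and correlations are planned for every visit. In the zero-correlation case a planned output would show a coefficient near 0. Retention comes from the same cross-classification. This stands, and it limits the point to the decision rule: informative measures are planned but have no part in the verdict.

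It is also fair that equal totals require an unshifted distribution, and that the outcome models and sample-size calculations use baseline fibrinogen directly and take no input from the stability verdict. No outcome estimate changes.

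A reader might infer three stronger points that the SAP does not support.

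- **That restriction to completers flatters stability.** The direction is not established. In an illustration with 50% high, correlation 0.6, 30% missing and a missingness odds ratio of 1.6 or 2.7 per SD of follow-up fibrinogen, completer retention is 66% or 61% against a true 70%, so completers look less stable. A likelihood model using all available visits gives 67% or 62%, so it does not cure missingness that depends on the unseen value. The restriction is attached only to the tabulation and CATMOD, not to the pairwise comparisons.
- **That the SAP flatly contradicts itself on missing data.** The general sentence ends by allowing for exceptions, and the acknowledgement in Analysis 2 can be read as one.
- **That Table 1 is wrong about Framingham.** The text may describe the source cohort rather than the integrated database, and no exam spacing is given. Only a need to reconcile the statements follows.

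**Conclusion.** The concern holds for the decision rule. The stated criterion compares marginal totals and does not test the within-patient assumption that it is meant to verify. If the fibrinogen distribution is unchanged between visits, the expected count difference is zero at every correlation, while retention at 50% high runs from 50% to 86%. At 20% high it runs from 20% to 75%. The rule favours 'stable' throughout, and it can also reject a marker whose patient ranking is unchanged.

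The equality of expected counts needs only an unchanged distribution. The retention figures rest on the assumed shares, the assumed correlations and bivariate normality, and are illustrations rather than predictions for ECLIPSE. Because no limit is set for an appreciable difference, the rule can be said to favour a verdict of stability but not to guarantee one.

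**What to change.** In Assessment of Key Assumptions, Analysis 2:

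1. Replace the count criterion with within-patient agreement at each threshold (250, 300, 350 and 400 mg/dL) and each visit (6 months, 1, 2 and 3 years). Report the share of baseline-high patients still high, with a 95% CI, together with kappa or specificity.
2. State in advance the limit against which these are judged, for example what lower confidence limit for retention and what kappa would support the statement that most patients keep their class.
3. For each visit use all patients with a baseline value and a value at that visit. Keep the all-visits tabulation and the CATMOD analysis as supportive.
4. Beside each figure report deaths and other losses among baseline-high patients, and do not claim that this removes bias from non-random missingness.
5. Separately, reconcile the Framingham description in Currently Available Data with Table 1 and with the statement that only ECLIPSE is longitudinal.

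The cost is a rewording and a few tables from data already held, largely built on outputs already planned. The downside is that the stability statement may become less favourable.

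### Two of the ECLIPSE fibrinogen-stability analyses drop every patient with a missing visit, although the SAP itself says these patients are not missing at random

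*SAP*

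**What the plan says.** In the SAP's Assessment of Key Assumptions, item 2 of the Analyses tests whether patients classed as high at baseline stay high over a trial-length period. It uses ECLIPSE, with measurements at baseline, 6 months, 1, 2 and 3 years. Four parts matter here.

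- **Main comparison.** The number and percentage high at baseline are set against later visits, with misclassification, sensitivity and specificity. Pearson correlations with baseline are given at each later time point. No completeness condition is attached to any of these.
- **Table of status at each time point.** "This analysis requires the exclusion of patients who are missing fibrinogen measurements at any time point for reasons which include death or other loss-to-follow-up". The next sentence reads: "As such, patients with missing fibrinogen measurements are not randomly missing". A summary of losses from death and other causes is to accompany the table.
- **PROC CATMOD model**, run at multiple visit lengths. "To perform an analysis of variance, only subjects with continuous visits are kept".
- **General default**, under General Statistical Considerations. "For all analyses, missing data will be considered randomly missing, and no data imputations or other algorithms for missing responses will be performed unless otherwise" (the sentence ends with the word indicated). The following sentence lets procedures such as analysis of variance drop subjects with missing data.

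On a separate matter, the Framingham entry under Currently Available Data says that "longitudinal measurements of plasma fibrinogen and lung function are available from two subsequent exam visits". Table 1 enters No for longitudinal fibrinogen in that cohort, and the stability section calls ECLIPSE "the only study with longitudinal fibrinogen measurements".

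**The concern.** Persistence of high status is one of two assumptions on which the SAP rests its use of the integrated database. An enrichment trial enrols patients at baseline. The status table and the CATMOD model describe patients who survived and attended without a gap.

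The selection is not neutral. All-cause mortality is one of the SAP's own outcomes, and its Background reports an association between raised fibrinogen and mortality in NHANES III. A patient who dies during year 3 can lose valid values at baseline, 6 months, 1 year and 2 years from the table.

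The exclusion is also avoidable. A frequency at a visit needs only the patients measured at that visit, and repeated-measures models for a binary status accept partial records. Having said that the loss is not random, the SAP names no analysis that deals with it. At stake are some precision and some bias in how stability is described.

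**Working it through.** The SAP gives no completer count, power or precision for the stability analyses, so there is no stated figure to reproduce.

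**Inputs from the SAP.** Table 1: 2,118 ECLIPSE COPD subjects and 220 deaths within 3 years. Four visits after baseline.

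**Assumptions.** All 2,118 have a baseline value, and a death within 3 years precludes the year-3 value. Among those alive, each later visit is missed independently with probability m. The SAP gives no m.

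**1. Loss from death alone.** 220/2,118 = 10.4%, so at most 2,118 − 220 = 1,898 patients (89.6%) have complete records.

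**2. Other missingness.** Completers = 1,898 × (1 − m)^4. Baseline-to-year-3 pairs = 1,898 × (1 − m). The ratio of standard errors, completers to available pairs, is the square root of pairs/completers = (1 − m)^(−3/2).

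| m | Completers | Share of 2,118 | Year-3 pairs | SE ratio, year 3 |
|---|---|---|---|---|
| 2% | 1,751 | 83% | 1,860 | 1.03 |
| 5% | 1,546 | 73% | 1,803 | 1.08 |
| 10% | 1,245 | 59% | 1,708 | 1.17 |

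At 6 months, if all 2,118 are still alive, available pairs number at most 2,118 × 0.95 = 2,012 or 2,118 × 0.90 = 1,906. The ratio is then at most √(2,012/1,546) = 1.14 or √(1,906/1,245) = 1.24.

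In absolute terms the loss is small. For a proportion of 50% and m = 10%, the year-3 standard error is √(0.25/1,245) = 1.4 points in completers, against √(0.25/1,708) = 1.2 points with available pairs.

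**3. Bias.** An illustrative simulation used 400,000 patients and five visits, normal fibrinogen with mean 400 and SD 100 mg/dL, threshold 350 mg/dL, and within-patient correlation 0.5 or 0.7. The log-odds of exclusion were 0, 0.3 or 0.6 per SD of the patient's average fibrinogen. All of these are assumptions. Completers were compared with the full simulated cohort.

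| Understatement in completers (log-odds 0.3-0.6) | 10.4% excluded | 30% excluded |
|---|---|---|
| Percentage high at baseline | 0.8-1.7 points | 2.4-5.0 points |
| Baseline-high still high at year 3 | 0.5-1.1 points | 1.3-3.4 points |
| High at every visit | 1.1-2.4 points | 3.1-6.5 points |

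With log-odds 0 there is no bias. Among completers the baseline and year-3 percentages stay together (for example 67.6% and 67.6%, or 64.3% and 64.3%). That agreement is partly built in, because the simulation has no time trend. The full cohort also carries values for patients who would have died, so these figures show an order of magnitude only.

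**The case against.** The strongest reply is that the restriction touches secondary pieces. A reader might infer that stability as a whole is judged in completers only. The text does not support that: the comparison that carries the stability criterion, the sensitivity and specificity, and the correlations have no such condition. This reply stands and limits the point to one table and one model.

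A reader might also see a flat contradiction between "For all analyses, missing data will be considered randomly missing" and "patients with missing fibrinogen measurements are not randomly missing". The general rule allows for exceptions, and the stability section can be read as one. What remains is that the exception is declared without a method to handle it.

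The SAP also discloses the problem and plans a summary of losses. That is fair, but the summary does not restore the discarded measurements.

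For CATMOD, multiple visit lengths may mean complete up to each length, not complete through year 3. The wording does not settle this, so the year-3 completer counts are firm for the table and only one reading for the model.

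A table of whole sequences of high and low would need complete records. The SAP, however, describes a frequency at each time point, which does not.

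Finally, the alternatives have assumptions of their own. Mixed models and dropout weighting rely on missingness at random, unweighted GEE needs more, and no method supplies fibrinogen after death. This is why results should be interpreted among those alive and shown with sensitivity analyses.

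**Conclusion.** The point holds for the high/low table and the PROC CATMOD model. Both discard measured values from patients who later die or drop out, the SAP acknowledges for the table that this loss is not random, and the exclusion is not needed.

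The size is modest. At most about 1,898 patients can have complete records. Under 5-10% assumed other missingness per visit, about 1,546-1,245 do, with year-3 standard errors about 8-17% above those from available pairs. A reader might instead compare completers with 2,118 patients at every visit and obtain 1/√0.730 to 1/√0.588, a rise of 17-30%. That comparator includes patients who have died, and no analysis could achieve it.

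If exclusion depends on fibrinogen, the percentage high is understated by about 1-2 points at 10.4% excluded, and by more with heavier loss. A reader might infer that the restriction makes fibrinogen look falsely stable. In the scenarios run, retention of high status is understated, and a reversal of the stability conclusion is unlikely, although the SAP sets no numerical limit for an appreciable difference. The change should be made because it is cheap and gives a better answer, not because the conclusion is in danger.

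The Framingham inconsistency is real but separate, and it says nothing about bias from excluding incomplete records.

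**What to change.** 1. Tabulate high and low at each visit among all patients measured at that visit, with died and missing as separate categories, so that each column accounts for the whole baseline cohort.
2. Make GEE or mixed logistic regression for high/low status, on all available measurements, the main longitudinal model, interpreted among those alive. Keep two sensitivity analyses: inverse-probability-of-dropout weighting, and the completer PROC CATMOD model with its completeness rule stated for each visit length.
3. State that the baseline-versus-later comparisons, sensitivity, specificity and correlations use all available baseline-to-visit pairs.
4. In General Statistical Considerations, exempt this analysis from the random-missingness default and refer to the methods above.
5. Separately, reconcile the Framingham description with Table 1 and the stability section. If repeat values exist within a relevant time window, report that cohort's stability as well (145 COPD subjects in Table 1). If not, correct the description.

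The cost is SAP wording and a different SAS procedure. No new ECLIPSE data are needed.

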## Objectives

The specific objectives for this analysis are to:

1. Verify the integrity of the integrated database
2. Describe the demographic and clinical characteristics of patients in the integrated database
3. Evaluate methods of defining patients with COPD
4. Assess longitudinal variation in plasma fibrinogen between individuals and within individuals
5. Define a cut point for classifying patients as having high fibrinogen levels
6. Assess the relationship between fibrinogen and risk of mortality and hospitalized COPD exacerbations during relevant time windows

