## 1.2. Baseline clinical characteristics

*Analyses:*

Descriptive statistics for baseline clinical characteristics in each dataset and combined datasets will be computed. Results will report mean (SD), median, and range (minimum to maximum) for continuous variables and frequencies (count and percentage) for categorical variables. The distribution of fibrinogen will additionally be summarized using interquartile ranges and the geometric mean, to better describe the skewed nature of the data.

*Variables:*

- Plasma fibrinogen
- Spirometry

- Pre-bronchodilator Forced Expiratory Volume in 1 second (preFEV1)
- preFEV1 (% predicted)
- Pre-bronchodilator Forced Vital Capacity (preFVC)
- preFVC (% predicted)
- preFEV1/FVC ratio
- Post-bronchodilator Forced Expiratory Volume in 1 second (postFEV1)
- Post-bronchodilator Forced Vital Capacity (postFVC)
- postFEV1 (% predicted)
- postFVC (% predicted)
- postFEV1/FVC ratio
- COPD exacerbations
  - Hospitalization
  - Death
  - Reported exacerbation

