### Objectives:

These analyses will:

- Compare COPD definitions using pre- and post-bronchodilator spirometric data within the ECLIPSE and COPDGene data.
- Assess longitudinal variation in plasma fibrinogen within individuals and between individuals using data from ECLIPSE.

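### Objective 4 is only partly answered: the plan measures change of fibrinogen class, but no analysis estimates within- or between-person variation on the fibrinogen scale

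*SAP*

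**What the plan says.** Item 4 of the SAP's Objectives is "Assess longitudinal variation in plasma fibrinogen between individuals and within individuals". The Objectives under Assessment of Key Assumptions repeat it: "Assess longitudinal variation in plasma fibrinogen within individuals and between individuals using data from ECLIPSE". Item 2 of the Analyses in that chapter carries the same aim in its heading and gives two reasons for it. One is to "determine if patients can be meaningfully categorized into groups of those with 'high' and normal levels of fibrinogen" over the length of a trial. The other is that a single value may suffice "if it can be determined that the variability among fibrinogen measurements is not clinically important over time". No limit is set for what would be clinically important.

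The longitudinal analyses that follow, all in ECLIPSE, are of two kinds:

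- **On high/low status:** numbers and percentages high at baseline and at later visits; error rates with sensitivity and specificity at each threshold; a tabulation of status across visits, repeated for each threshold; and a model fitted with PROC CATMOD: "A categorical analysis of variance (ANOVA) will be used to assess the variability of fibrinogen over time". For that model, "To perform an analysis of variance, only subjects with continuous visits are kept".
- **On the continuous values:** scatter plots of baseline against 6 months and 1, 2 and 3 years, and "Pearson correlation coefficients will be calculated to assess the correlation between baseline and subsequent fibrinogen levels at each time point".

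Descriptive Analyses, section 1.2, adds the interquartile range and geometric mean of baseline fibrinogen to the usual mean (SD), median and range, "to better describe the skewed nature of the data". No log scale is stated for the correlations.

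**The concern.** The objective asks for an amount of variation, split into a part within patients and a part between them. None of the listed methods returns that split. A correlation expresses one part relative to the other. A model of high/low status discards the size of each patient's change.

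At stake is the test that the plan sets for itself. To judge whether intra-patient variability is small enough to rely on one screening value, one needs its size as an SD or CV, together with any drift over time. Without these, the report can say how often patients changed class at 250, 300, 350 or 400 mg/dL. It cannot say whether those changes were small movements near a cut-point or large ones, or carry the result to another threshold.

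**Working it through.** **Step 1. Match each planned longitudinal analysis to what it yields.**

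| Planned analysis | Yields | Within-person SD/CV? | Between-person SD? |
|---|---|---|---|
| Percentages high by visit | Net change in class frequency | No | No |
| Error rates, sensitivity, specificity, tabulation | Individual change of class at four thresholds | No | No |
| PROC CATMOD | Change in class, subjects with continuous visits only | No | No |
| Scatter plots, Pearson r | Relative association with baseline | No | No |

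The baseline SD and interquartile range describe total spread across patients, which mixes the two components.

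**Step 2. What r leaves open.** The SAP states no mean, SD or correlation for fibrinogen, so there is no figure to reproduce and all inputs below are assumptions. Write each value as mean + patient effect (SD σ_b) + visit-level deviation (SD σ_w). With stable mean and variance, r = σ_b² / (σ_b² + σ_w²), so σ_w = total SD × √(1 − r).

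- r = 0.7, total SD 45 mg/dL: 45 × √0.3 = 24.6
- r = 0.7, total SD 90: 90 × √0.3 = 49.3
- r = 0.7, total SD 135: 135 × √0.3 = 73.9
- Total SD 90, r from 0.4 to 0.9: σ_w runs from 69.7 down to 28.5

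**Step 3. The same within-person variation, different r.** Fix σ_w at 0.15 on the log scale, a CV of √(exp(0.15²) − 1) = 15%. For σ_b of 0.10, 0.15, 0.20 and 0.25, σ_b² / (σ_b² + 0.15²) is 0.31, 0.50, 0.64 and 0.74. The coefficient more than doubles although no patient's own variability has changed.

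**Step 4. A common shift.** Assume total SD 90, r = 0.7 and a rise of 50 mg/dL in everyone at the later visit. Pearson r stays at 0.70. Counting the shift as within-person change:

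- Within-person mean square: 90² × 0.3 + 50²/2 = 2,430 + 1,250 = 3,680, an SD of 60.7 against 49.3 without the shift.
- Between-person mean square: 2 × (5,670 + 1,215) = 13,770.
- One-way ICC: (13,770 − 3,680) / (13,770 + 3,680) = 0.58.

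A model with visit as a fixed effect puts the 50 mg/dL in the visit means and leaves the within-person SD at 49.3.

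**Step 5. What class change leaves out.** Assume log-normal values, median 400 mg/dL, total log-SD 0.25, ICC 0.8 and no drift. Given a baseline value x, the later log value has mean ln 400 + 0.8 × ln(x/400) and SD 0.25 × √(1 − 0.8²) = 0.15. The chance of being above 350 mg/dL later is then about 60% for x = 355, 81% for x = 400 and 94% for x = 450. Sensitivity and specificity average over everyone on one side of the cut and do not show this gradient. Variance components do.

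**The case against.** A reader might infer that Pearson r and the categorical model measure nothing relevant and that Objective 4 goes unanswered. The SAP does not support that.

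- The error rates, sensitivity, specificity and tabulation measure individual change of class. Categorising patients is one of the two stated reasons for the analysis, and it is what key assumption 2 is about. This stands.
- With stable mean and variance, r equals the ICC, so it carries the relative split. Because the baseline SD is also reported, a reader could compute SD × √(1 − r) by hand. This stands as an approximation, but it needs equal variances at every visit, comes without a confidence interval and is not a planned output.
- The ICC shares r's dependence on spread, as Step 3 shows, and an ICC from a model with a fixed visit effect is equally blind to a common shift. This stands. The gain lies in the SDs, CVs and visit means.
- The skewness matters little for r: under the Step 5 assumptions, r on untransformed values is within about 0.01 of its log-scale value.

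It is also tempting to argue that a high r would hide patients dropping below the threshold. Under the Step 5 assumptions, a common fall of 0%, 10% or 20% leaves r near 0.80, while the share of those high at 350 mg/dL who stay high goes from 87% to 72% to 50%. This does not show the plan failing. The percentage high at the later visit would go from 70% to 54% to 36%, and the plan's stability criterion compares these percentages. The retention itself comes from the same two-by-two table as the planned error rates. Nothing in the SAP suggests such a fall.

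**Conclusion.** The point holds in a limited form. Change of class at the four thresholds is covered. The amount of within- and between-person variation, which Objective 4 names and which the plan makes the condition for relying on one measurement, is not estimated by any listed analysis. Objective 4 is therefore partly answered.

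The size of the gap can only be illustrated: for one value of r, the within-person SD varies threefold (24.6 to 73.9 mg/dL) over the assumed range of total SD. These figures rest on assumed distributions, since the SAP gives none, and they are not predictions for ECLIPSE. That no variance component is planned does not depend on those assumptions. The change is worth making because a stated objective lacks its matching estimate and the remedy is cheap.

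**What to change.** In Assessment of Key Assumptions, Analyses, item 2, add a linear mixed model of log fibrinogen in ECLIPSE. Use all available visits (baseline, 6 months, 1, 2 and 3 years), with visit as a fixed effect and a random patient intercept. Report:

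- visit means, as the measure of drift;
- within-person and between-person SD, also as CV;
- the ICC;
- 95% confidence intervals for these.

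Name the within-person SD/CV and the drift as the key outputs, because the ICC also depends on how varied the cohort is. Keep the reclassification measures, the Pearson coefficients and the PROC CATMOD model as complementary analyses. The coefficients at successive visits also give a check on the equal correlation over time that a random intercept implies.

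The cost is SAP wording and one further SAS model on data already in the integrated database. There is one real drawback. The model takes visits as missing at random given the observed values, while the SAP itself says that missing measurements in this analysis are not random because of death and other loss to follow-up. Add an explicit caveat or a sensitivity analysis by dropout status.
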